#### **4.3.9 Electrocardiogram**

Electrocardiograms will be obtained prior to the first cycle, middle of the first cycle (between C1D8-C1D16), at prior to the initiation of the second cycle. During the study, electrocardiogram will be assessed by the treating physician. If there are grade 2-4 cardiac toxicities the patient will be referred to cardio-oncology. At the end of the study cardio-oncology will review and tabulate results of QTc interval in all electrocardiograms (three per patient: one at baseline, cycle 1 day 8-16 and prior to initiation of cycle 2).

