### **1.2.2 Pharmacokinetics**

According to the FDA label for ribociclib, repeated 600 mg once daily administration, steady-state was achieved after 8 days; the time to reach maximum concentration is between one and four hours after administration of ribociclib; the half-life of ribociclib is 32 hours (14).

The FDA label indicates clinical activity is primarily due to the parent drug and ribociclib is metabolized to other compounds that have a negligible contribution on clinical activity. The primary metabolic pathways of ribociclib include oxidation, N-acetylation, sulfation, cysteine conjugation, glycosylation, and glucuronidation (14). Ribociclib is the major circulating drug in plasma, accounting for 44%, however there is a possible contribution to ribociclib effect from circulating metabolites: M13 represents 22% of ribociclib exposure, M4 accounts for 20% and, M1 for 15% (14). Ribociclib is eliminated mainly via feces with a small contribution from the renal route (14).

Ribociclib undergoes hepatic metabolism mainly via CYP3A (14). Ritonavir is a strong CYP3A inhibitor, when ritonavir was given in combination with ribociclib there was an increase of the maximum concentration ( $C_{max}$ ) and the area-under-the-curve (AUC) of ribociclib increased by 1.7 and 3.2-fold, respectively (14, 15). Ribociclib in combination with erythromycin, a moderate CYP3A inhibitor, the  $C_{max}$  and AUC of the CDK 4/6 inhibitor increased by 1.3 and 1.9-fold, respectively (14). The opposite effect in ribociclib concentrations was noted with CYP3A inducers, such as rifampicin (14).

\* The magnitude of extrahepatic FMO1 contribution is unknown

James, A.D., et al. *Pharmacol Res Perspect.* (2020).

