## 2.4 Secondary Endpoints

1. Ribociclib pharmacokinetic properties: maximum concentration ( $C_{max}$ ), the time to reach  $C_{max}$  ( $T_{max}$ ), AUC, clearance, volume of distribution( $v_d$ ), elimination half-life, and mean residence time (MRT) at steady state (visit between days 8-16 of cycle 1).
2. Change in QTc interval between:
  - 1) baseline and between days 8-16 of cycle 1,
  - 2) baseline and scheduled visit prior to initiation of cycle 2
3. Laboratory abnormalities: neutropenia, ALT, and AST, between
  - 1) baseline and between days 8-16 of cycle 1,
  - 2) baseline and scheduled visit prior to initiation of cycle 2

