
Electrocardiograms (ECGs) should be assessed prior to initiation of treatment. Repeat ECGs at approximately Day 14 of the first cycle and at the beginning of the second cycle, and as clinically indicated.
 
*QTcF = QT interval corrected by Fridericia's formula.
	

Table 8: Dose Modification and Management for AST or ALT Elevations

	Grade 1 (> ULN – 3x ULN)	Grade 2 (> 3 to 5x ULN)	Grade 3 (>5 to 20x ULN)	Grade 4 (> 20x ULN)
AST and/or ALT elevations from baseline*, WITHOUT total bilirubin increase above 2x ULN	No dose adjustment required	Baseline* at < Grade 2: Dose interruption until recovery to ≤ baseline grade, then resume ribociclib at same dose level. If Grade 2 recurs, resume ribociclib at next lower dose level Baseline* at Grade 2: No dose interruption	Dose interruption until recovery to ≤ baseline* grade, then resume at next lower dose level. If Grade 3 recurs, discontinue ribociclib.	Discontinue ribociclib
Combined elevations in AST and/or ALT WITH total bilirubin increase, in the absence of cholestasis	If patients develop ALT and/or AST > 3 x ULN along with total bilirubin > 2 x ULN irrespective of baseline grade, discontinue ribociclib.			
Abbreviations: AST, aspartate aminotransferase; ALT, alanine aminotransferase; ULN, upper limit of normal. *Baseline = prior to treatment initiation.				

Table 9: Dose Modification and Management for Blood bilirubin increased without AST/ALT increase

Toxicity/Grade	Recommendations
Blood bilirubin increased without AST/ALT increase	
Grade 1: >ULN - 1.5 x (upper limit of normal) ULN if baseline was normal; > 1.0 - 1.5 x baseline if baseline was abnormal	Maintain dose level with LFTs monitored bi- weekly.
Grade 2: >1.5 - 3.0 x ULN if baseline was normal; >1.5 - 3.0 x baseline if baseline was abnormal	Dose interruption of ribociclib. If resolved to ≤ grade 1 in ≤ 21 days, then maintain dose level. If resolved to ≤ grade 1 in > 21-28 days or toxicity recurs, then reduce 1 dose level. Repeat liver enzyme and bilirubin tests twice weekly for 2 weeks after dose resumption. If toxicity recurs after two dose reductions, or recovery to ≤ grade 1 is > 28 days, discontinue ribociclib.

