e Clinical Visits: clinical visits will include medical history, vital signs and physical exam and will be conducted as per local practice and as clinically indicated. Physical Examination includes a general clinical examination of major body systems.

f To be performed after informed consent and used for screening according to sections 3.6 and 4.3.7. CYP3A5 Screening may be bypassed per Principal Investigator discretion if the necessary number of participants with each phenotype are enrolled (cohort of AA or Black participants - at least 3 poor metabolizers; cohort of NHW participants - at least 3 intermediate or normal metabolizers). If CYP3A5 is already performed it does not need to be repeated within the window of  $\leq$  28 days.

g All patients will receive ribociclib plus physician choice endocrine therapy with fulvestrant or letrozole. Luteinizing hormone-releasing hormone (LHRH) agonist (goserelin or leuprolide) will be required for premenopausal women.

h To be performed at these times per routine clinical practice and the treating physician: prior to treatment initiation; repeat on day 8-16 of cycle 1, and prior to initiation of cycle 2

i To be performed at these times per routine clinical practice and the treating physician: baseline, repeat on day 8-16 of cycle 1, and prior to initiation of cycle 2

j To be performed at these times per routine clinical practice and the treating physician: Pregnancy test (serum or urine), required for women of childbearing potential

k Questionnaires to be completed within 28 days of C1D1

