## 9.2 Statistical Analysis Plan

Primary analyses will be performed as follows. Within each race-based cohort, the ribociclib exposure which measured by ribociclib AUC will be summarized by median [Interquartile range, IQR], and two-sample t-test if normality holds or Wilcoxon-Mann-Whitney test will be used to compare AUC between CYP3A5 poor metabolizers and CYP3A5 intermediate or normal metabolizer in each independent race-based cohort. Secondary analyses will be performed as follows. Descriptive statistics will be used to characterize the data profile, frequency and percentages for categorical variables, and mean (SD) or median [IQR] for continuous variables based on the data normalization. Multiple regression will be used to identify variables associated with ribociclib AUC. To best account for any factor that may affect ribociclib exposure, covariates to be assessed include CYP3A5 metabolism status, renal function, liver function, age, race, weight, sex, among others. Any covariates with  $P < 0.2$  on univariate analysis will enter the stepwise multiple linear regression model, with  $P < 0.05$  considered statistically significant. This methodology will also be used to assess a change in absolute neutrophil count and QTc as the outcome variable. Depending on data distribution, a two-sample t-test or Wilcoxon-Mann-Whitney test will be used for 1) a change (baseline and C1D8-C1D16) in continuous variables (e.g., QTc, absolute neutrophil count) between CYP3A5 poor metabolizers and CYP3A5 intermediate or normal metabolizers, 2) to check the association between a continuous variables and categorical risk factors. Pearson correlation coefficient or Spearman correlation coefficient will be calculated to measure the association between two continuous variables. Fisher's exact test will be used for checking the association between two categorical variables. AEs will be assessed with descriptive statistics and univariate logistic regression will assess the occurrence of specific AEs with pharmacokinetic properties (e.g., AUC,  $C_{max}$ ). The approach from the linear regressions will be adapted to logistic regression to identify covariates associated with the occurrence of grade III or IV neutropenia.

Descriptive analysis of the PRO-CTCAE adverse event log to determine frequency of adverse events by race and by CYP3A5 genotype.

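### The day 8-16 ECG behind the QTc endpoint has no set time after dosing, so timing alone can move ribociclib concentration at the ECG by up to about 1.5-1.6-fold

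*Combined protocol and SAP*

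**What the plan says.** All references are to the combined protocol and SAP.

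- **When the ECG is taken.** Section 4.3.9 sets the second of three ECGs for the "middle of the first cycle (between C1D8-C1D16" window. Footnote h to Table 14 (Section 6.1) leaves it to local routine and the treating physician: "prior to treatment initiation; repeat on day 8-16 of cycle 1, and prior to initiation of cycle 2". Table 7 (Section 5.4) reads differently: "Repeat ECGs at approximately Day 14 of the first cycle". Sections 4.1 and 7.1.2 repeat the day window. None gives an hour after dose or ties the ECG to a PK sample.
- **How the PK samples are timed.** Section 4.3.8 takes them before the dose and at 0.5, 1, 2, 4 and 6 h after it, with windows of 5 or 15 minutes.
- **What the ECG is used for.** Section 2.4 makes QTc change a secondary endpoint, "baseline and between days 8-16 of cycle 1" being the first of two comparisons. Section 9.2 tests "a change (baseline and C1D8-C1D16) in continuous variables (e.g., QTc, absolute neutrophil count) between CYP3A5 poor metabolizers" and expressors, and also makes QTc a regression outcome. Section 2.3 compares toxicity, including QTc prolongation, between the race cohorts. No adjustment for time since dose is planned.
- **What is recorded.** The dosing log in Appendix 14.3 asks for date, amount and comments. No section lists the clock time of the dose or of the ECG as an item to collect.

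**The concern.** Section 1.5 states that higher exposure is associated with a prolonged QTc interval, and the study is built to relate exposure to phenotype. A QTc reading is easiest to interpret when it is known where on the concentration curve it was taken. Here one patient may be read just before a dose and another near peak, and the data set may not show which.

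This single reading carries most of the QTc information. Ribociclib stops after day 21 (Section 5.3.1), so the later ECG cannot back up a poorly placed mid-cycle one. The smaller phenotype group in each cohort may hold only 3 patients (Section 3.3), so one ECG can carry a third of that group's mean. Meanwhile the patient is already on site from before the dose to 6 h after it for PK sampling.

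**Working it through.** The documents give no figure for exposure at the ECG and no power for QTc, so there is no plan figure to reproduce.

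**Inputs.** Section 1.2.2: "the half-life of ribociclib is 32 hours", and "the time to reach maximum concentration is between one and four hours after administration of ribociclib". Section 5.3.1: one dose every 24 h, days 1 to 21. Table 14 footnote b: final visit at day 29 ± 3.

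**1. Peak against trough, simple decline.** Ratio = 2^((24 − Tmax)/32).
- Tmax 1 h: 2^(23/32) = 1.65
- Tmax 2 h: 2^(22/32) = 1.61
- Tmax 4 h: 2^(20/32) = 1.54

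**2. Check with a one-compartment oral model at steady state.** C(t) ∝ e^(−kt)/(1 − e^(−24k)) − e^(−ka·t)/(1 − e^(−24ka)), with k = ln2/32 and ka solved to give the stated Tmax.

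| Tmax (h) | ka (/h) | Peak/trough | SD of log2 C, times even over 24 h | Max/min, 1-6 h | Max/min, 2-4 h |
|---|---|---|---|---|---|
| 1 | 4.44 | 1.64 | 0.21 | 1.11 | 1.04 |
| 2 | 1.77 | 1.59 | 0.20 | 1.08 | 1.03 |
| 4 | 0.64 | 1.49 | 0.18 | 1.16 | 1.05 |

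A pre-dose ECG at the PK visit restores the full peak-to-trough range.

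**3. Does the choice of day matter?** Fraction of steady state after d days = 1 − 2^(−24d/32): 97.4% at d = 7, 98.4% at d = 8, over 99.9% at d = 15. Hardly at all. The spread comes from the hour, not the day.

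**4. Size of the noise.** For scale only, take the planning SD of 0.75 log2 units (Section 9.1, set for AUC). Adding the timing SD gives √(0.75² + 0.18²) = 0.77 to √(0.75² + 0.21²) = 0.78. With 3 against 15 patients, the SD of the chance difference in timing between groups is 0.18 × √(1/3 + 1/15) = 0.11 to 0.21 × 0.632 = 0.13 log2 units, or about 8% to 10% in concentration.

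**5. Is the other on-treatment ECG a substitute?** Day 29 ± 3 is 26 − 21 = 5 to 32 − 21 = 11 days after the last scheduled dose. Remaining fraction = 2^(−24 × days/32): 2^(−3.75) = 7.4% at 5 days, 2^(−6) = 1.6% at 8 days, 2^(−8.25) = 0.3% at 11 days. That reading is essentially off drug.

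**6. Sensitivity to half-life** (assumed values, simple decline, Tmax 4 h and 1 h): 24 h gives 1.78 to 1.94; 48 h gives 1.33 to 1.39.

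**The case against.** The strongest case on the other side has four parts.

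- **The fold figure is an extreme.** It compares one patient exactly at peak with another exactly at trough. Typical spread is much smaller, as step 4 shows. This stands, and it is why the figure is stated as an upper limit.
- **The ECG probably falls at the PK visit anyway.** Table 14 puts the ECG, PK samples and questionnaires in one day 8-16 column, and the adverse event log has a single mid-cycle visit. An ECG taken 1 to 6 h after the dose would vary only about 1.08- to 1.16-fold. This is a fair reading, but footnote h does not require it, and a pre-dose ECG at that visit remains allowed.
- **No concentration-matched QTc analysis is planned, and QTc can still be related to AUC.** True. The gap means only that a paired concentration is not assured.
- **The mid-cycle ECG is also a safety ECG**, and Table 7 places it near day 14. This stands as a point to reconcile.

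A reader might go further and infer that a true 2-fold exposure gap would shrink, to 2/1.64 = 1.22 or 2/1.49 = 1.34. That requires poor metabolizers at trough and expressors at peak. The reverse pairing widens the gap by the same factor, and nothing in the documents links ECG timing to phenotype. Timing could follow site practice, and sites may differ in racial mix, but the documents give no ECG practice by site, so confounding with race is a possibility and not a finding.

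**Conclusion.** The point holds as a cheap improvement to a secondary endpoint. Timing alone can move concentration at the day 8-16 ECG by up to about 1.5-1.6-fold. If ECG times were even over 24 h, the added SD would be about 0.18-0.21 log2 units: modest noise without a systematic direction. It is worth removing because no other scheduled ECG after baseline is on drug and the smaller group may be 3 patients.

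The figures rest on a single 32 h half-life, one-compartment kinetics and uninterrupted dosing to day 21.

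Two stronger conclusions are not supported. First, the 2-fold target in Section 9.1 belongs to AUC, which comes from dose-timed samples, so the primary endpoint is unaffected and the fold range should not be set against that target. Second, no loss in milliseconds of QTc can be stated: the documents give no concentration-QTc slope, no QTc SD, and nothing on whether QTc follows plasma concentration without delay.

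**What to change.** In Section 4.3.9 and Table 14 footnote h, state that the mid-cycle ECG used for the QTc endpoint is recorded at the PK visit, next to one fixed post-dose sample. The 2 h or 4 h sample would serve; as an illustration, variation across a 2-4 h window is only about 1.03- to 1.05-fold. Record the clock times of that day's dose and of the ECG on the CRF, and add to Section 9.2 that time since dose or the paired concentration may be used in the QTc analysis. If the placement cannot be adopted, recording the two times alone would still allow adjustment.

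Reconcile the new wording with the day 14 wording in Table 7, and leave clinically indicated ECGs unchanged.

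Cost: protocol wording, two CRF fields, and booking the routine mid-cycle ECG on the PK day. No extra ECG is needed where that visit serves as the mid-cycle ECG visit.

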#### **4.3.10 Adverse Event Assessment**

Baseline symptoms at cycle 1 day 1 (prior to initiating therapy) should be detailed and graded. Once treatment has started, AEs will be assessed every 2 weeks during the first cycle. The individual Investigator should record any AE in detail including the date of onset, event diagnosis (if known) or sign/symptom, severity, time course, duration and outcome, relationship of the AE to study drug, and any action(s) taken. AE grade (Based on the CTCAE 5.0) and start date will be documented in the adverse event monitoring form ([Appendix 14.6](#)). Patients will be followed for one cycle.

See section 8 for adverse event monitoring and reporting. The Principal Investigator or sub-Investigators will assess AEs, laboratory data, and vital signs throughout the study. AEs will be assessed by NCI CTCAE Version 5.0. AEs, whether in response to a query, observed by site personnel, or reported spontaneously by the patient will be recorded. All AEs will be followed to a satisfactory conclusion.

#### **4.3.11 Removal of Patients from Study**

Each patient has the right to withdraw from study treatment at any time. In addition, the Investigator may discontinue a patient from the study treatment at any time for any reason if the Investigator considers it necessary, including the occurrence of an AE or noncompliance with the protocol.

Each patient will be withdrawn from study treatment if any of the following occur:

- The patient requires radiotherapy or alternate antineoplastic agents during the study period
- The investigator believes it is in the best interest of the patient
- Clinically significant deterioration of the patient's medical status as determined by the investigator
- Any other medical reason that the study investigator deems appropriate

#### **4.3.12 Discontinuation of Individual Patients**

When a patient discontinues the study treatment (without reaching a protocol-defined endpoint), the investigator will notify the Principal Investigator as soon as possible (provided, in each case, patient care and safety are not compromised). When a patient discontinues the study treatment, a final visit will be conducted, preferably prior to the initiation of another anticancer therapy. However, these procedures should not interfere with the initiation of any new treatments or therapeutic modalities that the investigator or patient's treating physician feel is necessary to treat the patient's condition. Following discontinuation of the study drug, the patient will be treated in accordance with the investigator's/treating physician's best clinical judgment.

At the final visit, the reason(s) for the discontinuation from the study will be recorded and a physical examination, body weight, vital signs measurement, laboratory analyses, performance status, tumor assessment, and an assessment of AEs will be performed as soon as possible after discontinuation from the study treatment. If a patient is discontinued from the study with an ongoing AE or an unresolved clinically significant laboratory result, the site will attempt to provide follow up until a satisfactory clinical resolution of the laboratory result or AE is achieved.

#### **4.3.13 Patient Replacement Criteria**

If a patient is enrolled but is unable to tolerate ribociclib or to participate in laboratory workup and cardiac studies as well during cycle 1, she would be deemed non-evaluable. In the case of an unexpected trauma or death that is considered unrelated to the underlying solid tumor malignancy, patient would be deemed to be non-evaluable.

#### **4.3.14 Discontinuation of the Entire Study**

The Investigators may terminate this study provided that written notice is submitted at a reasonable time in advance of the intended termination. The following procedures for discontinuation will be followed:

1. If the Investigators have decided to prematurely discontinue the study, the Investigators will promptly notify in writing the IRB of the decision and give detailed reasons for the discontinuation.
2. The Principal Investigator must promptly notify the enrolled patients of the premature discontinuation and administer appropriate treatments such as replacement of protocol therapy, if applicable, by other appropriate regimens.

#### **4.3.15 Protocol Deviations**

The Investigator should not implement any deviation from the protocol without prior review and in accordance with the IRB and local regulations, except when necessary to eliminate an immediate hazard to study patients.

## **5 Study Treatments**

## **5.1 Allocation to Treatment**

Following full assessment and determination that the patient meets all eligibility criteria and has given informed consent for study participation; the investigator or designee will contact the study principal investigator (PI) or designee and request study enrollment. A patient identification number will be assigned, which must be used on all CRF pages and on all documentation and correspondence referencing that patient.

## **5.2 Compliance**

Drug accountability will be performed at every visit during the first cycle (Appendix iii). The number of remaining capsules (of ribociclib and letrozole) will be documented and recorded to assess compliance.

The following paragraph is also discussed in the informed consent form. Patient's or their insurance company will have to pay for the prescribed medications as they are part of standard care. However, the first 28-day cycle of their treatment with ribociclib will be paid for through a voucher. Neither the patient nor insurance company would be charged for the first 28-day cycle of ribociclib. This is expected to cover the cost of the ribociclib for the duration of the study. More details about the voucher are available here: <https://mprsetrial.mckesson.com/7426/#>. If the patient and their physician choose to continue using ribociclib beyond the first cycle then it would lead to added costs for the patient and/or their insurance company.

## **5.3 Drugs**

The drugs used in the course of this trial will be ribociclib and letrozole or fulvestrant as well as a luteinizing hormone-releasing hormone (LHRH) agonist (i.e., goserelin, leuprolide) for premenopausal women. These drugs are commercially available drugs and will be prescribed by their oncologist.

### **5.3.1 Ribociclib**

Commercially available Ribociclib 600 mg (3 x 200 mg tablets by mouth) QD on days 1 to 21 of a 28-day cycle, followed by 7 days off ribociclib (Days 22 to 28).

### **5.3.2 Fulvestrant**

Commercially available fulvestrant will be used. Locally obtained commercial supplies of fulvestrant will be used in accordance with local regulations.

### **5.3.3 Letrozole**

Commercially available letrozole will be used. Locally obtained commercial supplies of fulvestrant will be used in accordance with local regulations.

